5.3. Ophthalmic procedures

5.3.1. Grading Cataracts

The study ophthalmologist will grade cataracts at every clinical exam based on the Age-Related Eye Disease Study (AREDS) clinical lens grading system (Chew et al., 2010). Pupils must be dilated maximally and lenses should be examined at the slit lamp for the presence and severity of three types of opacity: nuclear, cortical and posterior subcapsular. For each type of opacity, the examiner should compare the lens being examined with the AREDS 2008 Clinical lens opacity standard photographs, of increasing severity. In each series, "1" indicates clinical presence, "2" indicates clinical significance, and "3" indicates severe occurrence. Half grades may be given, for example if a nuclear opacity was thought to be half way between the first and second standard photographs, a decimalized grade of "1.5" could be assigned.

The study ophthalmologists will refer to laminated photos of the scale in real time when making the clinical assessment. If no cataract is present, he/she will indicate this on the clinical exam form.

The following categories of severity are present for all types of opacity (nuclear, cortical and posterior subcapsular): <1, 1, 1.5, 2, 2.5, >3.

*Clinical grading adapted from: Chew EY, KIM J, Sperduto RD et al. Evaluation of the Age-Related Eye Disease Study Clinical Lens Grading System AREDS Report No. 31. Ophthalmology 2010; 11; 2112-2119.

5.3.2. Grading inflammation

Slit lamp examination and dilated fundusoscopic exam are important parts of our study: assessments of anterior chamber cells and vitreous haze will determine the patient’s course of treatment. All of our study physicians are fellowship-trained uveitis specialists who have participated in prior uveitis studies.

The study ophthalmologist at each site will be required to perform an eye examination at each study visit. This examination should be similar to that performed in the routine care of uveitis patients. Several components will be assessed in detail per study protocol. The grading schemes to be used for these assessments are adapted from the Standardization of Uveitis Nomenclature (SUN) Working Group.²

Anterior Chamber Cells

SUN Working Group Grading Scheme for Anterior Chamber Cells

Grade	Cells in Field*
0	<1
0.5+	1-5
1+	6-15
2+	16-25
3+	26-50
4+	>50

*Field size is a 1mm by 1mm slit lamp beam. Grading should be done with the highest magnification and illumination and conducted in a completely dark room, prior to dilation.

Anterior Chamber Flare

Anterior Chamber Flare will be assessed by slit lamp exam but will not be part of our study criteria for controlled inflammation.

SUN Working Group Grading Scheme for Anterior Chamber Flare

Grade	Description
0	None
1+	Faint
2+	Moderate (iris and lens details clear)
3+	Marked (iris and lens details hazy)
4+	Intense (fibrin or plastic aqueous)

*Adapted from: Hogan MJ, Kimura SJ, Thygeson P. Signs and symptoms of uveitis: I. Anterior Uveitis. AM J Ophthal 1964;47:155-170; Grading should be conducted in a completely dark room

Vitreous Cells

There is currently no accepted standard for grading vitreous cells, which will not be part of our study criteria for controlled inflammation. However, we will collect this information using the grading scheme below, which is adapted from the [REDACTED]:

Grade	Cells in Field*
0	No cells
0.5+	0 to 5 cells
1+	6-10 cells
2+	11-20 cells
3+	21-50 cells
4+	>50

*Field size is a 1mm by 0.5mm beam; Grading should be conducted in a completely dark room; These cells are graded by slit lamp exam after dilation.

Vitreous Haze

Vitreous haze will be assessed using an indirect ophthalmoscope set at mid-power and a 20D lens. Fundus examination will be done with the last view being the area around the optic disc. The examiner should then compare this view to the photograph (Figure 1) and determine the level of vitreous haze. The National Eye Institute System for grading vitreous haze will be used for all primary and secondary outcome measures. Additionally, vitreous haze will be assessed separately on the 9-point grading scale recently published by Davis et al., known as the Miami scale. The examiner should compare the vitreous haze view with the Miami photograph. An exploratory analysis will correlate measurements from the NEI and Miami scales. Clinical measurements of vitreous haze will also be compared to objective assessments done by grading of fundus photos by the reading center.

If the physician thinks that the grading of vitreous haze is affected by a significant media opacity (i.e. a dense/mature cataract) they should indicate on the Clinical Exam Form that they cannot make a reliable judgment of vitreous haze due to the opacity.

[figure not shown]
Figure 1: National Eye Institute system for grading vitreous haze

Grade	Description
0	Clear
0.5+	Slight blurring of optic disc margin Normal striations and reflex of nerve fiber layer cannot be visualized
1+	Opacities without obscuration of retinal details
2+	Few opacities resulting in mild blurring of details of optic nerve and retinal vessels
3+	Optic nerve head and retinal vessels significantly blurred but still visible
4+	Dense opacity obscuring optic nerve head

*Grading should be conducted in a completely dark room; From Nussenblatt et al. Standardization of vitreal inflammatory activity in intermediate and posterior uveitis. Ophthalmology 1985;92:467-471.

Figure 2: Miami 9-point system for grading vitreous haze

Miami Scale for photographic grading of vitreous haze in uveitis. Am J Ophthalmol;150:637-641 e1.

Grading Retinal/Choroidal Inflammation

Assessment of active inflammation of the retina and choroid should be based on the clinical exam and ancillary testing if needed for certain diseases (i.e. fluorescein angiogram, fundus photography, B-scan ultrasound). Please refer to the table in Appendix F for imaging required for assessing uveitis activity by disease.

Active vasculitis posterior to the equator qualifies as active inflammation, but according to SUN criteria should be confirmed with a fluorescein angiogram. Macular edema in isolation is not sufficient to qualify as active inflammation, but a bullous serous retinal detachment, with any amount of accompanying vitreous, retinal or choroidal inflammation would qualify as an active inflammation. In addition, per protocol, if patients have $\geq 1+$ anterior chamber inflammation, vitreous haze and/or other retinal/choroidal lesions aside from macular edema, that would qualify as active as well.

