4.2. Study form completion schedule

Forms	PHASE I					PHASE II				
	Baseline : Phase I	Week 2	Follow up months 1-5, 9	Treatment Failure anytime*	Follow up months 6 & 12	Baseline: Phase II**	Week 2	Follow up months 1-5	Treatment Failure anytime*	Follow up month 6
Eligibility/ Screening Form	X									
Consent Form	X									
Baseline History Form	X									
Clinical Eye Exam Form	X		X	X	X			X	X	X
Secondary Clinical Eye Exam Form	X			X	X				X	X
Visual Acuity Form	X		X	(x)	X			X	(x)	X
OCT Form	X		X	(x)	X			X	(x)	X
Fundus Form	X			(x)	X				(x)	X
Laboratory Report Form	X	X	X	(x)	X		X	X	(x)	X
Adverse Event Checklist		X	X	X	X	X	X	X	X	X
Vision Related Quality of Life	X			X	X				X	X
Health Related Quality of Life	X			X	X				X	X
Treatment Assessment Form	X	X	X	X	X	X	X	X	X	X
Patient Calendar***		X	X	X	X		X	X	X	X
Medication Log	X	X	X	X	X	X	X	X	X	X
Patient Dropout	(x)	(x)	(x)	(x)	(x)	(x)	(x)	(x)	(x)	(x)
Protocol Deviation Form	(x)	(x)	(x)	(x)	(x)	(x)	(x)	(x)	(x)	(x)
Adverse Event Narrative	(x)	(x)	(x)	(x)	(x)	(x)	(x)	(x)	(x)	(x)
Adverse Event Log	(x)	(x)	(x)	(x)	(x)	(x)	(x)	(x)	(x)	(x)

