***Note that treatment failure may be declared at a scheduled study visit or at a non-study visit;**

All (x) are only to be filled out if applicable.

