- If the box is mounted on a movable stand, the 4-meter distance must be marked clearly and permanently. The location and orientation of the box must be rechecked each time a new chart is put in place or the box is touched. When the stand touches the rear wall of the room, two of the five casters should touch the wall.

1 Meter

- The 1-meter distance is measured from the eye of the subject, who is seated comfortably in a chair with his or her back firmly placed against the chair's back, to the center of the second (for testing the left eye) or fourth letter (for testing the right eye) of the third line of the chart. A stick, one meter long, should be used to confirm the distance for each subject.

Visual Acuity Procedure

- Visual acuity will be measured at each study visit.
- Visual acuity should be measured for each eye AFTER refraction. Visual acuity should NOT be recorded during the refraction procedure.
- It is very important that the examiner is not aware of the patient's clinical records, in order to minimize bias. Therefore, the visual acuity examiner will not have access to the patient's previous clinical examination or treatment results.
- Visual acuity is tested separately for each eye (one eye at a time). The patient's untested eye will be completely covered with a patch, to block out all light from entering this eye. The examiner must constantly ensure that this eye remains occluded at all times.
- The patient is instructed to read each letter on the chart starting with the largest line, at the 4-meter distance.
- The patient will show the orientation of the tumbling "E" with the hand that they are not using to occlude the untested eye. If the patient cannot identify the orientation of a letter, they are encouraged to guess. **Only one response is allowed per letter.**
- The examiner must ensure that the patient does not squint (creating a pin-hole effect) or lean forward (reducing the distance to the chart).
- Once a patient has given a response for a letter and has moved on to provide a response for the next letter, any corrections of previous response will not be accepted.
- However, if the patient has given a response for a letter and has not yet moved on to provide a response for the next letter, a correction of the previous response is accepted.

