5.3.3. Inter-observer variation of ocular inflammation

At Baseline (Phase I and Phase II) the 6th month study visit (Phase I and Phase II), the 12th month study visit (Phase I), or at treatment failure (whichever is earlier), inter-observer agreement on slit lamp observations and fundoscopic exam will be assessed. Coordinators will arrange for two certified study physicians to measure anterior chamber cells, anterior chamber flare, vitreous cells, vitreous haze, and retinal/choroidal lesions at the Month 6 and 12 visit or at declaration of treatment failure. The inter-observer variation will be reported. The primary study ophthalmologist's measurements will be used for primary analysis.

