9.9. OCT Operators

- Perform OCT photography as specified by protocol of both eyes at all visits

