Assessment and follow-up depends on the status of the eye. Eyes classified as type E above are recorded as such at baseline, and never provide eye outcome related data. Because (a) inability to assess parts of the eye could be related to the progression of disease, but (b) inability to assess in the absence of signs of disease cannot be considered evidence of treatment failure, we use the following table to summarize how success at six months will be scored. In this table, the row corresponds to the status of an eye at baseline, and the column to the status of the eye considering the primary outcome of success at six months.

	Month 6: A	Month 6: B	Month 6: C	Month 6: D	Month 6: E
Baseline: A	Success	See below**	Fail	Fail	Fail*
Baseline: B	Success	See below**	Fail	Fail	Fail*
Baseline: C	Success	See below**	Fail	Fail	Fail*
Baseline: D	Success	See below**	Fail	Fail	Fail*
Baseline: E	NA	NA	NA	NA	NA

Specifically, note that an eye which is fully assessable at six months and which does not meet the specific criteria for failure of control is always considered a success. Eyes which are fully or partially assessable and which meet any of the criteria for failure are always considered to have failed. However, eyes which are only partially assessable but which meet no criteria in the assessable region may be scored successes or failures depending on their baseline status (see next paragraphs below). Eyes which were present at baseline but which are missing at the end of the study are listed as Fail* in the table; we propose to consider such eyes to have failed unless a specific reason demonstrates that the loss of the eye was completely unrelated to the presence or progression of disease.

The primary analysis is at the patient level. Both eyes must meet the success criteria for the patient to be considered a success.

****Incompletely assessable eyes.** Uveitis assessment for this purpose is based on (i) assessment of anterior cells, (ii) vitreous haze, and (iii) retinal or choroidal lesions. In the pilot study, (iv) assessment of vitreous cells was also used. We will have longitudinal measurements of inflammation according to the following schedule: anterior chamber cells, vitreous haze and

active retinal/choroidal lesions will be measured at Baseline, Week 2, Month 1 and every subsequent 4 weeks until the 6 month assessment (Phase I or Phase II) or 9 and 12 month assessment (Phase I 6-12 months).

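### The form schedule omits the Week 2 eye exam that the protocol text and SAP call for, and lets a patient start Phase II with no acuity or OCT measured near that date

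*Combined protocol and SAP*

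**What the plan says.** The narrative sections and the SAP set broad measurement rules.

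- Protocol 5.3.2, eye exam: "The study ophthalmologist at each site will be required to perform an eye examination at each study visit".
- Protocol 5.2.2.A and 5.2.2.B, acuity: "Visual acuity will be measured at each study visit".
- Protocol 9.9, OCT: "Perform OCT photography as specified by protocol of both eyes at all visits".
- Protocol 4.4.1 and 4.4.3 list exam, acuity and OCT for follow-up visits and do not exempt Week 2, which Table 9 makes a scheduled visit (±3 days) in both phases.
- Protocol 5.3.3 opens its list of two-examiner grading visits with "At Baseline (Phase I and Phase II) the 6th month study visit (Phase I and Phase II".
- SAP 3.1 says that cells, haze and "active retinal/choroidal lesions will be measured at Baseline, Week 2, Month 1 and every subsequent 4 weeks until the 6 month assessment", in Phase I or Phase II.

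The form schedule in 4.2 is narrower. The "Clinical Eye Exam Form" row and the acuity and OCT rows are blank at Week 2 in both phases and at Phase II Baseline. At treatment failure the exam is marked X, but acuity and OCT are marked (x), and the note under the table says that such forms "are only to be filled out if applicable". Sections 4.6.1 and 4.6.3 leave acuity and OCT out of the minimum set for a failure declared at a non-study visit. Phase II may start up to two weeks after failure (4.1.2, 4.5).

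**The concern.** Coordinators complete the forms that 4.2 lists, so where it is narrower than the text, what is collected depends on which part of the manual a site follows. There are two consequences.

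**Week 2 inflammation.** The SAP expects these readings. They feed time to first control (SAP 3.2.2, item 2), the worst-value rule for parts of an eye that cannot be assessed (SAP 3.1) and the multiple-imputation covariates (SAP 3.5).

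**Acuity and thickness at Phase II start.** SAP 2.3.2 carries all the six-month secondary objectives of Aim 1 into Aim 2, and SAP 3.4.2 says they will be analysed by similar methods. Those include change in acuity from baseline (3.2.2, item 4) and macular thickness adjusted for baseline (item 9). Neither section says which measurement is the Phase II baseline. Any gaps would fall on patients who fail between scheduled visits or very early, who are a selected group. The conditional mark at failure also touches Aim 1, because SAP 3.2.1 and 3.2.2 take acuity at the time of failure as the final value for patients who fail.

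**Working it through.** **1. Is the schedule read correctly?** Each row of the 4.2 table splits into ten cells, five per phase.

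| Form | I: Base | Wk 2 | M1–5, 9 | Failure | M6, 12 | II: Base | Wk 2 | M1–5 | Failure | M6 |
|---|---|---|---|---|---|---|---|---|---|---|
| Clinical exam | X | – | X | X | X | – | – | X | X | X |
| Secondary exam | X | – | – | X | X | – | – | – | X | X |
| Acuity | X | – | X | (x) | X | – | – | X | (x) | X |
| OCT | X | – | X | (x) | X | – | – | X | (x) | X |
| Laboratory | X | X | X | (x) | X | – | X | X | (x) | X |
| AE checklist | – | X | X | X | X | X | X | X | X | X |

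The laboratory and adverse-event rows are filled at both Week 2 columns, so the blanks above them are not a shift in the extracted table. Under the schedule, one of the eight Phase I assessments up to Month 6 (Baseline, Week 2, Months 1–6) carries no inflammation data.

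**2. When could control first be recorded?** With a Week 2 exam: about day 14 (window day 11–17). Without it: Month 1. Its window is about day 30 ± 15, or day 15–45. Section 4.1.1 also requires two weeks between visits, so for a patient who attends Week 2 the earliest day is 11 + 14 = 25. The range is about day 25–45.

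**3. Which time-to-event analysis is affected?** SAP 3.2.2 makes first steroid-sparing control the principal one. In Table 6, 60 mg is held for 2–4 weeks, then ten one-week steps lead to 7.5 mg: 2 + 10 = 12 to 4 + 10 = 14 weeks. On that taper steroid-sparing control at Week 2 is not expected. The loss falls on the separate analysis of first control of inflammation.

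**4. How can a Phase II patient lack acuity and OCT?**

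- Failure at a scheduled visit in Months 1–6: both forms are X. No gap.
- Failure at a non-study visit: the required minimum is the clinical eye exam; acuity and OCT are (x).
- Failure at Week 2, which 3.1.1 and 3.1.2 foresee for early intolerability: acuity and OCT are blank in the Week 2 column and (x) in the failure column.
- Phase II starting the same day: the failure column applies and nothing is added. Starting up to 14 days later: the Phase II Baseline column has no acuity or OCT form.

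In the second and third cases both measurements can be absent while every required form is complete.

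**5. How many?** SAP 3.4.2 gives expected Phase II enrolment as patients randomized per arm × retention × failure fraction:

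- 108 × 0.9 × (1 − 0.4) = 58.3
- 108 × 0.9 × (1 − 0.6) = 38.9
- total 97.2

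Both terms match the SAP table. The documents give no rate of failure at non-study visits. Assuming 5–20%, and that none of those patients has acuity or OCT obtained: 0.05 × 97.2 = 4.9 to 0.20 × 97.2 = 19.4, or about 5–19. This is a ceiling for that assumed range of non-study failures. Week 2 failures are not counted separately.

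**The case against.** The best defence is that the schedule governs and the safeguards are adequate.

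- Sections 5.2.3.A and 5.2.3.B send the reader to the form schedule for the timing of acuity, and 9.9 makes OCT subject to the protocol. This softens the acuity and OCT conflict. It does not resolve Week 2 inflammation, where 4.4.3, 5.3.2 and SAP 3.1 stand against 4.2 with no such deferral. It also sends sites to the version that omits the measurements.
- A reader might infer that Phase II patients can start with no inflammation grading. The documents do not support that. Clinical and secondary exams are both X at failure, at most about 14 days before Phase II, and Phase I accepts a baseline exam of the same age. Section 5.3.3 also asks for two graders when failure is declared, so its mention of Phase II baseline needs only alignment.
- A reader might infer that some patients will in fact lack acuity and thickness. The documents show only that they can. Section 4.6.1 asks sites to try for the full set of procedures at a non-study failure, 4.6 prefers failures to be declared at scheduled visits, and laboratory SAE failures do not enter Phase II (5.6).
- Earlier Phase I values exist, and SAP 3.2.2 carries acuity forward when vision cannot be assessed, with mixed-model sensitivity analyses. This helps in part. No equivalent rule covers thickness, no earlier value is named as the Phase II baseline, and SAP 3.5 itself calls carrying observations forward unhelpful during a steroid taper.
- SAP 3.2.2 already plans an interval-censored analysis of time to success, and Week 2 is blank in both arms. Both points limit the damage to the time analyses.

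**Conclusion.** The inconsistency is real and should be corrected; its reach is limited. Week 2 inflammation will be collected only where sites follow the text. The main effect is on time to first control of inflammation, where the first recordable date moves from about day 14 to about day 25–45. The effects on the worst-value rule and the imputation covariates are minor. A patient failing at a non-study or Week 2 visit can enter Phase II with no acuity or OCT at or near that date, which weakens Aim 2 acuity change and baseline-adjusted thickness. The same gap can leave Aim 1 without acuity at the time of failure.

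The number affected is unknown. About 5–19 of 97 is an upper figure that rests on the SAP's enrolment projection, an assumed 5–20% of failures at non-study visits, and no acuity or OCT being obtained at any of them. It would be tempting to read this as a threat to the primary comparison. It is not: the exam is required at Month 6 and at failure, so the Month 6 primary outcome is largely untouched.

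**What to change.** **Phase II baseline.** In 4.2, and in the minimum sets of 4.6.1 and 4.6.3, make the acuity and OCT forms required at the Phase I failure visit or, if not obtained there, at the separate-day Phase II Baseline. State in SAP 2.3.2 and 3.2.3 that the failure-visit or Phase II Baseline measurement, taken within the 14 days before Phase II start, is the Phase II baseline for acuity, thickness and inflammation.

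**Week 2.** Choose one of two routes:

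- add the Clinical Eye Exam Form to both Week 2 columns of 4.2, and except Week 2 from the acuity and OCT rules; or
- delete Week 2 from SAP 3.1, and except that visit in 4.4.1, 4.4.3, 5.2.2, 5.3.2 and 9.9.

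Under either route, align 5.3.3 with 4.2 on the Phase II baseline grading.

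**Cost.** Text edits in several sections of the protocol and SAP, and a few more acuity and OCT forms at visits already held. The first Week 2 route also adds one exam form per patient per phase, for an exam that the text already requires.

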5.3.3. Inter-observer variation of ocular inflammation

At Baseline (Phase I and Phase II) the 6th month study visit (Phase I and Phase II), the 12th month study visit (Phase I), or at treatment failure (whichever is earlier), inter-observer agreement on slit lamp observations and fundoscopic exam will be assessed. Coordinators will arrange for two certified study physicians to measure anterior chamber cells, anterior chamber flare, vitreous cells, vitreous haze, and retinal/choroidal lesions at the Month 6 and 12 visit or at declaration of treatment failure. The inter-observer variation will be reported. The primary study ophthalmologist's measurements will be used for primary analysis.

5.3.4. Training and certification of ophthalmologists and study coordinators

All exams must be performed by uveitis specialists. The study protocol and classification system for grading inflammation will be reviewed by [REDACTED] (or another study ophthalmologist from [REDACTED]) with the investigators at all sites. An open-book exam on the study protocol will be administered, and a score of 80% is needed for

certification to participate in the trial. For investigators with scores less than 80%, additional instruction and a re-test will be done. Prior to study start, each site investigator will grade inflammation on 5 uveitis patients and scores will be compared to the [REDACTED] investigator's scores. If a discrepancy of greater than 1 grade in any of the measurements occurs, then additional patients will be graded until there are 5 consecutive patients where the grade is within 1 level for each of the measurements (i.e. anterior chamber cells, vitreous haze, and retinal/choroidal lesions). If both graders assess each area to have 0 inflammation in a particular patient, that patient would not count towards the 5 patients needed to complete the training. This grading assessment will be done prior to initiation of the trial and yearly thereafter. Duplicate measurements of inflammation will also be collected at the 6 and/or 12-month study visits. Inter-observer agreement will be reported.

The study protocol will be reviewed with all study coordinators by coordinating center personnel. An open-book exam on the study protocol will be administered, and a score of 80% is needed for certification to participate in the trial. For coordinators with scores less than 80%, additional instruction and a re-test will be done.

